6 STUDY DESIGN

Protocol CELIM-RCD-002 is designed to be a Phase 2a randomized, double-blind, placebo-controlled, parallel-group study to evaluate the efficacy and safety of AMG 714 for the treatment of adult patients with RCD-II, an in situ small bowel T cell lymphoma.

After signing consent, subjects will be screened for the study. All subjects who meet the study entry criteria will be randomized 2:1 ratio to receive either 8 mg/kg AMG 714 or placebo a total of 7 times over 10 weeks, with evaluation of the primary endpoint at Visit 8 (Week 12/Day 84).

AMG 714 (N=16) or placebo (N=8) will be administered at the clinical site in a double-blind fashion via intravenous (IV) infusion of approximately 120 minutes (2 hours) duration.

Subjects will remain confined to the study site for a minimum of 1 hour after the administration of study medication. During this time the Investigator and study site staff will assess the subject for AEs. As per Table 1, PK samples are to be collected prior to the infusion and 1 hour after the infusion, at the end of this observation period. The beginning and end of the infusion, as well as the PK sample collection times, will be recorded.

In addition to receiving study medication (AMG 714 or placebo), concomitant therapy with steroids at a maximum dose of 20 mg of prednisone, prednisolone or equivalent per day and/or oral budesonide at a maximum dose of 9 mg per day will be accepted. Steroid doses must be stable for 4 weeks prior to randomization and remain stable for the duration of the study. Budesonide has been used in RCD-II with improvement of symptoms and is considered adequate background therapy for RCD-II (Brar *et al*, 2007).

Should AMG 714 show adequate efficacy and safety, as determined by the Sponsor, subjects in the study, including those in the placebo arm, may be offered participation in an open label extension study of AMG 714 in due course, but under no circumstances prior to study completion. In the interim, between the end of the study for an individual subject and the start of the possible open label extension, the Sponsor intends to provide a bridging program to allow objective study responders to have access to AMG 714 as determined by their site investigator or physician. The open label extension study and interim bridging program will be described in independent protocols.

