13 EFFICACY ASSESSMENTS

13.1 IMMUNOLOGICAL RESPONSE: ASSESSMENT OF ABERRANT INTRAEPITHELIAL LYMPHOCYTES

The primary endpoint in this trial is the reduction in the % of aberrant intestinal IELs with respect to total IELs as assessed by flow-cytometry (Immunological Response 1). The first secondary endpoint is Immunological Response 2, the reduction in the % of aberrant intestinal IELs with respect to intestinal epithelial cells, a composite endpoint calculated by multiplying the % of aberrant IEL vs total IELs (determined by flow cytometry) by the % of total IEL vs intestinal epithelial cells, as assessed by immunohistochemistry. The secondary endpoint could be more representative of a benefit driven by functional impact rather than simple reduction in IEL numbers.

Both endpoints address the core abnormality in RCD-II, an in situ small bowel T cell lymphoma in which aberrant lymphocytes are responsible for mucosal damage and symptoms and for the progression to EATL. Aberrant IELs are described as surface CD3-negative, intracellular CD3-positive. The reduction in the proportion and number of aberrant lymphocytes is specific to RCD-II, is analogous to a reduction in tumor size in a solid tumor cancer, and has been proposed as the most direct measurement of efficacy in RCD-II (as reviewed in van Wanrooij *et al.*, 2014).

This exploratory study, first industry-sponsored trial in RCD-II, will be considered positive for the purposes of Go-No decision-making if at least one of the two calculations of Immunological Response is found to be positive.

Flow cytometry is the most accurate tool available to quantify aberrant IELs (van Wanrooij *et al.*, 2014), and it is preferred over IHC, (less sensitive) and TcR rearrangement or clonality by polymerase chain reaction (PCR, less specific) (van Wanrooij *et al.*, 2014). Enumeration of total IELs will be done by IHC to calculate the secondary endpoint of % of aberrant IELs vs intestinal epithelial cells. Enumeration of aberrant (intracellular CD3) and abnormal (altered phenotype, such as overexpression of NKG2D) IELs by IHC and PCR will be performed as well, as exploratory endpoints.

Flow cytometry of IELs requires the acquisition of fragment(s) of small bowel tissue by endoscopy and biopsy, and the method to disperse, stain and analyze the IELs is described elsewhere (Leon, 2011).

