13.2 HISTOLOGIC RESPONSE: SMALL BOWEL ENDOSCOPY, BIOPSY AND HISTOLOGY

At each time point specified in Table 1, small-bowel biopsies will be collected in order to perform the aberrant IEL analysis and the histological assessment of mucosal inflammation. The latter will provide the secondary endpoint of Histological Response, as measured by improvement from baseline in small intestinal VH:CD ratio assessed with a validated morphometric analysis (Taavela *et al*, 2013). Lack of Histological Response has been shown to correlate with long term outcomes including progression to EATL (Nijeboer *et al*, 2015 a, b), albeit the current Phase 2a study may be of insufficient duration to fully assess histological recovery (slower than immunologic resolution). In addition to the VH:CD ratio, the second commonly used histological score, the Marsh-Oberhuber classification (Marsh, 1992, Oberhuber 2000), as well as the total IEL count (all IEL, not just aberrant) will also be calculated as a secondary endpoint.

At each time point specified in Table 1, approximately eleven to thirteen (11-13) fragments or specimens of small-bowel tissue will be taken from the second part of the duodenum distal to the ampulla by trans-oral upper endoscopy and forceps biopsy. Biopsies should be collected from the D2 segment of the duodenum. Ulcerative lesions should be avoided. The location and macroscopic appearance of the tissue will be noted in the source documents. The potential presence of any observable lesion such as ulcerative jejunitis will be captured in the eCRF. When necessary, samples will be re-oriented and sectioned again until they are of good quality. The procedures will be described in a Study or Laboratory Manual or similar document, and the IEL/LPL preparation method will be based on published methods by the Paris site. The fragments or specimens will be prioritized as follows:

- i. First five specimens collected, for flow cytometry: Approximately 5 biopsy specimens will be used for flow cytometry, done locally at each site with fresh tissue.
- ii. Second three specimens collected, for histology and immunohistochemistry: Approximately three (3) biopsy specimens will be fixed in 10% formalin or other fixative, with one (1) of them used for standard pathology at the site and two (2) of them embedded in paraffin wax after orientation for analysis

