22.2 POPULATIONS FOR ANALYSIS

The populations for analysis will be intention to treat (ITT, safety population who at least received one dose of investigational product) and the per protocol population (PP, efficacy, i.e., available and evaluable pre- and post-biopsy information).

PP Population: The PP population will exclude non-evaluable subjects and subjects with major protocol deviations thought to impact the ability to assess the effect of treatment. Exclusion of subjects from the PP set will be reviewed, documented and approved before the study is unblinded to the study Sponsor. The criteria for excluding subjects from the PP population will be specified in the SAP.

ITT (Safety) Population: This population consists of all randomized subjects who have received at least one dose of the study drug. Subjects will be analyzed in the treatment group they were randomized to. Subjects with only one measurement available will be excluded from the ITT population for all endpoints defined as change from baseline. The safety population is by definition the same as the ITT population.

Main efficacy measures which require pre- and post-treatment biopsies will be based on the PP population (at least 2 biopsies, the second at least on Week 6 or later). Continuous variables will be analyzed based on the ITT population. Demographics and safety parameters will be analyzed using the ITT population.

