8.1 Data sets to be analysed

The populations for analysis will be the intention to treat (ITT, safety population, at least one dose of the investigational product received) and the per protocol population (PP, efficacy, i.e., available and evaluable pre- and post-biopsy information [Week 6]).

PP population: the PP population will exclude non-evaluable subjects and subjects with major protocol deviations thought to impact the ability to assess the effect of treatment. The PP population will also exclude atypical RCD-II patients (patients with a different phenotype of the aberrant IELs) for the purpose of analysis of Immunological Response 1 and 2; however, they will be included in all other efficacy assessment where a sensitivity analysis maybe performed excluding these subjects if these subjects are determined to be influential. Exclusion of subjects from the PP set will be reviewed, documented and approved before the study is unblinded to the study Sponsor.

Non-evaluable subjects will include subjects missing one of the two biopsies (or with biopsies of insufficient quality to generate valid data as determined by the Sponsor prior to database lock) and subjects dropping out of the study before Week 6. If a discontinuation occurs on or after Week 6 and the second biopsy is collected, then the subject is considered evaluable.

Atypical patients may also be analysed as a separate population if the results and sample size suggest such analysis is valuable.

The following major protocol deviations, as determined by the Sponsor prior to database lock, will lead to exclusion of subject from the PP population and will be thoroughly documented in the clinical study report:

- Intake of any forbidden concomitant medication or participation in other medical procedures, in case there is reason to believe, by the judgement of the Sponsor or investigator, that such concomitant medication/procedures would have a significant effect on the efficacy data obtained;
- Significant deviations from the inclusion/exclusion criteria of the study not previously approved by the Sponsor and determined prior to database lock to have impact on interpretation of results.

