8.6 Analysis of efficacy

8.6.1 Primary efficacy variable

Primary efficacy endpoint of the study is:

- Immunological Response 1: Relative (%) change from baseline to Week 12 in the % of aberrant intestinal intraepithelial lymphocytes (IELs) vs total IELs as assessed by flow-cytometry.

The primary endpoint will be analysed using analysis of covariance (ANCOVA), where the baseline % aberrant IELs vs total IELs will be included as a covariate and treatment group as a fixed effect in the statistical model.

The analysis of the primary endpoint will be carried out using the PP population. Subjects having Week 6 biopsy data who are lost to follow-up for further visits will have their Week 6 value carried forward for the final analysis (more details available in *Chapter 8.2.2 Missing values*).

The following model will be fitted:

$$Y_{ij} = \mu + \beta \cdot \text{baseline \% IEL vs total IEL}_{ij} + \alpha_j + \varepsilon_{ij},$$

where

Y_{ij} is the relative (%) change from baseline in the % of aberrant IELs vs total IELs for subject i ($i = 1, \dots, n_j$) from treatment group j ($j = 1, 2$),

μ is the overall mean,

β is the parameter estimate of baseline % IELs vs total IELs,

α_j is the fixed effect due to treatment j ,

ε_{ij} is the random error for subject i from treatment group j ; $\varepsilon_{ij} \sim N(0, \sigma_\varepsilon^2)$.

The following SAS code will be used to fit the above-specified model (NOTE: SAS codes provided in this document may be modified based on statistical considerations, without requiring SAP amendment):

```
proc glm data=IELt alpha=0.1 outstat=F_tests;
  class trt;
  model IELt_change = bl_IELt trt / clparm solution SS1 SS2;
  estimate "AMG 714 vs Placebo" trt 1 -1;
  lsmeans trt /cl stderr alpha=0.05;
  ods output ParameterEstimates=Par_est LSMeanCL=LS_meanCL
             LSMeans=LS_mean OverallANOVA=ANOVA Estimates=Eff_est;
run;
```

The modelling results (ANOVA table, parameter estimates, estimated treatment effect, marginal (i.e. least squares) means estimates and results of the check of assumptions) will be tabulated and 90% confidence intervals added, where appropriate.

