8.9 Additional analyses

In addition to the main analyses, pre-specified subgroup analyses may include the following, if reasonable distributions of subgroups are available for statistically meaningful assessments:

- Dietary transgressions (gluten consumption) based on serial iVYLISA GIP testing and on the dietician's assessment;
- Previous RCD-II treatment (e.g. previous treatment with BMT, cladribine, steroids, Hu-Mik-beta1, etc.);
- Duration of disease;
- Age of onset of RCD-II;
- Sex;
- Site;
- Expression of certain biomarkers at baseline, such as CD122, Granzyme B and IL-21R in IELs, or IL-15 in serum;
- Levels of anti-tTG antibodies, at baseline and during the study;
- Protocol deviations: missed doses of IP, incorrect IP volume for administration, etc.;
- Use of immune-suppressants: concomitant or prior to the study (cladribine, azathioprine, budesonide, stem cell transplant, etc.).

These additional sensitivity analyses may be carried out only for the key flow cytometry and histology endpoints (i.e., the primary and secondary efficacy endpoints dependent on biopsy tissue). Separate models will be fitted for males and females, compliant and non-compliant subjects, subjects with each of the previous treatments, groups of subjects with different disease durations, groups of subjects with different age of onset of disease, and for each site. In order to determine whether the effects of sex, compliance and site are statistically significant, additional three models are fitted where compliance, sex and site and their interaction terms with treatment group, respectively, are included.

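### SAP 8.1 can drop subjects with two evaluable biopsies from the only primary-endpoint analysis on a judgement not stated to be blind to the flow result, and no committed analysis shows the effect

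*SAP*

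**What the plan says.** Protocol 22.2 hands the detail to the SAP: "The criteria for excluding subjects from the PP population will be specified in the SAP". SAP 8.1 then lists the major deviations that lead to exclusion. The lead-in gives the determination to the Sponsor before database lock, and exclusions must be approved before the Sponsor is unblinded. The first bullet covers forbidden medication or other medical procedures where it is thought, "by the judgement of the Sponsor or investigator, that such concomitant medication/procedures would have a significant effect on the efficacy data obtained". It makes no exception for a subject with both biopsies.

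SAP 8.6.1 names one set: "The analysis of the primary endpoint will be carried out using the PP population". Table 1 assigns the primary variable to PP, and its first footnote puts every biopsy-dependent variable there. The secondary run on absolute change repeats the model and names no other set. Immunological Response 2 is also on PP.

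On who may know the outcome, Protocol 13.2 says: "Approximately 5 biopsy specimens will be used for flow cytometry, done locally at each site with fresh tissue". Protocol 6 describes a "bridging program to allow objective study responders to have access to AMG 714 as determined by their site investigator or physician", available once an individual subject has finished.

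SAP 8.9 lists concomitant immune suppressants and protocol deviations among subgroup analyses that may be done, "if reasonable distributions of subgroups are available for statistically meaningful assessments". It names no population.

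**The concern.** Whether a subject counts in the primary analysis can turn on a judgement made after randomisation and possibly after that subject's result exists. The stated safeguards mask treatment. Neither document says that the people judging lack the second flow result, or that the judgement must be recorded before it.

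Need for extra steroids or immune suppressants is plausibly related to doing badly. If AMG 714 works, more of those subjects will be on placebo. Removing them makes the remaining placebo arm look better and shrinks the estimate. If the removed subjects happen to be on AMG 714, the estimate is inflated. Both Immunological Responses use this set, and under Protocol 13.1 the study is "considered positive for the purposes of Go-No decision-making if at least one of the two calculations of Immunological Response is found to be positive". With eight placebo subjects, one exclusion is visible in the estimate, yet no planned model is certain to show the result with and without it.

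**Working it through.** **Plan inputs** (Protocol 22.1, SAP 7): difference 20 percentage points (pp), common SD 17.4, 16 and 8 subjects, two-sided alpha 0.10, target power about 80%.

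**Reproducing the plan.** Noncentrality = 20 / (17.4 × √(1/16 + 1/8)) = 2.654. The critical t on 22 df is 1.717. Power is 82.3%, consistent with the stated figure.

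**Lost numbers only** (exclusion unrelated to outcome), same formula:

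| AMG 714 / placebo | Power |
|---|---|
| 15 / 8 | 81.5% |
| 13 / 8 | 79.4% |
| 16 / 7 | 79.1% |
| 16 / 6 | 75.0% |

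Losing one placebo subject, or three on AMG 714, takes power below 80%.

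**Leverage of one subject.** Removing a subject 20 pp worse than the arm mean moves that mean by 20/15 = 1.3 pp (AMG 714) or 20/7 = 2.9 pp (placebo).

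**Exclusion related to outcome.** The documents give no exclusion rate, no link to outcome and no rescue-drug effect, so all three are assumed. Reduction Y is normal with SD 17.4 and mean 20 (AMG 714, n = 16) or 0 (placebo, n = 8). The exclusion score is Z = ρ·Y/17.4 + √(1 − ρ²)·N(0,1). The k subjects with the lowest Z are the cases, ignoring arm. The test is a pooled t test at two-sided 0.10, with 200,000 simulated trials. Keep means retaining the k cases after adding a rescue-drug reduction of 20 pp, equal to the trial's target effect.

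| ρ | k | Exclude: mean, power | Keep: mean, power |
|---|---|---|---|
| 0.5 | 1 | 19.3 pp, 78.6% | 18.9 pp, 80.1% |
| 0.5 | 2 | 18.8 pp, 75.2% | 18.2 pp, 78.1% |
| 0.5 | 3 | 18.4 pp, 71.7% | 17.5 pp, 75.7% |
| 0.8 | 1 | 18.2 pp, 76.0% | 18.4 pp, 79.8% |
| 0.8 | 2 | 16.9 pp, 69.8% | 17.1 pp, 77.5% |
| 0.8 | 3 | 16.0 pp, 64.2% | 16.0 pp, 75.0% |

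Simulation error is about 0.1 pp in the means and a few tenths of a point in power. At ρ = 0 and a 20 pp rescue effect the two approaches have about equal power. At ρ = 0.5 the power advantage of keeping is nearly gone at a 25 pp rescue effect (78.9%, 75.5%, 72.3%) and reverses at 30 pp (77.2%, 72.2%, 67.4%).

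**No true effect.** Arm-blind exclusion leaves two-sided error at 9.9% to 10.1%. If every exclusion falls on AMG 714 (the worst-scoring one or two of 16, ρ = 0.5), the chance of a significant result favouring AMG 714 is 6.8% or 8.5%, against 5%.

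**A second rule, for direction.** Suppose a user is excluded only if the aberrant percentage did not fall, and 25% of placebo subjects but no AMG 714 subjects are users. The estimate moves by −2.0 pp, and with a true 20 pp effect power falls from 82% to 71%.

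**The case against.** **The bullet may catch few subjects.** Protocol 10.1 allows prohibited drugs to treat an adverse event, and use discussed with the medical monitor is not classed as a deviation. The SAP bullet sits in a list of major deviations, so approved use may leave the subject in PP. This stands: the number affected could be zero, which is why the extra run should be conditional.

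**The test concerns the drug, and the Sponsor decides.** The wording asks what the medication would do, and the determination precedes lock and unblinding. A reader might infer that investigators will exclude subjects according to their flow results. The documents do not show that. Local flow and site-identified responders make knowledge possible, no more, and the responder rules sit in separate protocols. What remains is that nothing rules it out.

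**The effect is not hidden.** Listings use ITT with PP flags, baseline and post-baseline primary values are listed, major deviations and population counts are tabulated, and exclusions are documented in the study report. With about 24 subjects, someone holding the listings could recompute the result. So it would be wrong to say readers cannot find out. It remains true that no committed analysis reports it.

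**Keeping rescued subjects is no cure.** Correct. At ρ = 0.5 and a 20 pp rescue effect, keeping them shrinks the estimate more than excluding them does, and its power advantage is only 1.5 to 4 points.

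**Conclusion.** The point holds as a gap in the sensitivity analysis and in the decision procedure. SAP 8.1 can remove subjects with two evaluable biopsies from the only committed analyses of Immunological Responses 1 and 2, by a judgement masked to treatment but not stated to be masked to outcome. SAP 8.9 does not fill the gap: its runs are optional, one to three users would hardly meet its condition, and Table 1 puts biopsy variables on PP.

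Two stronger readings are tempting. One is that the rule inflates false positives. It does so only if exclusions are unequal between arms, for which the documents give no basis, and it can equally work against AMG 714. The other is that PP is the wrong primary set. Neither set is unbiased, and PP was prespecified for an exploratory study.

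The power and error figures are illustrations under assumed exclusion counts, correlation and rescue effect. They are on the absolute-change scale. The SAP tests relative change and gives no SD for it, so they carry over only if the standardised effect (20/17.4 = 1.15) is similar. This is a cheap improvement worth making.

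**What to change.** 1. **SAP 8.6.1 and Immunological Response 2 in 8.6.2.** Keep PP as primary. If anyone is excluded under the medication/procedure bullet, also run the same ANCOVA on all dosed classic RCD-II subjects with two evaluable biopsies, ignoring that bullet, and report it beside PP. This is in line with the protocol's own ITT rule for change endpoints: "Subjects with only one measurement available will be excluded from the ITT population for all endpoints defined as change from baseline".

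2. **SAP 8.1.** Require the judgement to be made from drug, dose and dates, by people without that subject's second flow result, and recorded in the Subject Classification Document, which is already to be finalised before lock.

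Leave the reference to efficacy data as it stands, because VH:CD, Marsh score and total IEL counts share the PP set. Do not extend the bullet to monitor-approved use, which would widen the exclusion.

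Cost: a few SAP sentences and one rerun of an existing model for each of two endpoints, only if such cases occur. Both biopsies and concomitant medications are already collected. Downside: the extra run includes outcomes that a rescue drug may have changed, so its estimate may be diluted and must be read together with PP.

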8.2 General statistical considerations

Descriptive statistics (e.g. mean, median, standard deviation (SD), minimum (MIN), maximum (MAX), and number of subjects with an observation (N) or missing observation (NMISS)) are used for summarizing continuous variables. Additional statistics will be provided for PK-related data, including the geometric mean, SD of log-transformed data, geometric CV% and geometric N (i.e. number of subjects with an observation that are included in the natural logarithmic transformation).

Frequencies and percentages are used for summarizing categorical variables.

All summary statistics will be presented by treatment arm and if repeated measures, then by visit/collection time point.

All listings will be created using ITT population. The PP and ITT flags for each subject will be included in all listings.

All tests will be two-sided, if not stated differently. P-values smaller than 0.1 (for primary hypothesis) or 0.05 (all other hypotheses) will be considered statistically significant. In addition to the inferential statistics, 90% or 95% confidence intervals will be constructed. For the primary endpoint a 90% confidence interval of the treatment difference will be

constructed. Ninety-five percent (95%) confidence intervals will be constructed for the individual treatment point estimates.

